# Our hypothesis is that:

For patients who undergo lumbar spinal fusion surgery with interbody support, the outcomes in terms of pre-operative measures, intra-operative measures, and post-operative measures in the investigational group (BMAC + allograft) will be similar to the compared BMP group and control group at 24 months postoperatively.

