# **Study Objective**

To compare the efficacy of BMAC+allograft versus BMP versus autograft (control), we plan to pursue a prospective, blinded controlled study in which: BMAC+allograft or BMP or autograft will be randomized 1:1:1 ratio, respectively to certain patients undergoing a lumbar fusion by interbody support.

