### • Arthodesis rate one year post-operation (paired t-test):

The effect size (ES) in this study was 0.4, considered to be low using Cohen's (1988) criteria. With an alpha = .05 and power = 0.80, the projected sample size needed with this effect size is approximately N = 23.

Thus, our proposed sample size of N=60 (with 20 patients per arm; effectively 40 for t-tests between groups) will be more than adequate for the main objective of this study and should also allow for expected attrition

Completion rate of enrolled patients in our protocol is estimated to be 85% based on standard clinical follow up rates for lumbar Spinal Fusion patients at the investigators practices. Therefore, by enrolling 20, we expect at least 17 in each group.

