# **Data Analysis**

### Sample Size Justification

There are no previous studies with exact means in ODI for a BMAC group not the association between clinical outcomes and concentration of MSCs and CFUs. Therefore, assumptions had to be made. If the standard deviation for each group was assumed to be 10 and equivalence as within 12.8 (MCID), given 90% power and alpha=0.05, we would need 14 patients per group. However, if we assume equivalence as within 6 points, we would need 59 patients per group. We understand that assumptions greatly affect sample size, and therefore, our desired sample size of 60 patients is appropriate.

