# Aim 1: Clinical Study

This study will analyze the clinical and radiographic outcomes in terms of pre-operative measures, intra-operative measures, and post-operative measures followed-up for in the three groups.

Primary Outcome Endpoint: As per the primary outcome measure, fusion status at 1 year will be assessed via CT scan by an independent radiologist. Clinical outcomes will be defined by patient reported and health-related quality of life measures previously defined. Differences from preoperative visit to post-operative time points will be compared between the 3 groups by Student t-tests. Based on preliminary data, improvements are expected in these outcome measures: ODI from 33.42 (SD:6.22) to 26.75 (SD:8.19); SF-12 PCS from 29.00 (SD:6.05) to 31.42 (SD:6.05); SF-12 MCS from 31.42 (SD: 6.50) to 35.75 (SD: 13.82); NRS from 8.17 (SD: 1.27) to 5.93 (SD: 1.90). Multivariate regression analysis, controlling for age, sex, race, and charlson comorbidity index, will be performed to determine the effect of treatment on reaching MCID values, as defined in Parker et al 2012.[2]

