### Aim 2: Basic Science Study

Lab analysis of aspirate quality will quantify density of CBC + differential (WBCs, platelets, Hct...), CD34+ cells, cell viability and CFU-f,,Mesenchymal Stem Cells, Colony-Formung Units, CD13, CD 14, CD29, CD34, CD44, CD45, CD73, CD90, and CD105. One-way ANOVA and Student's t-tests will compare significant values between the 3 groups

The lab analysis will be performed as per routine practice Harvest Technology, a Terumo BCT company.

PI: [name]

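### Aim 1 clinical outcomes: about 75 pairwise t-tests across three arms, five visits and about five instruments, with no overall test, lead comparison or error control

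*Combined protocol and SAP*

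**What the plan says.** The Study Objective has three arms: "BMAC+allograft or BMP or autograft will be randomized 1:1:1 ratio". Under Data Analysis, Aim 1, the primary outcome is fusion on CT at 1 year, and no test is assigned to it there. The clinical outcomes follow: "Differences from preoperative visit to post-operative time points will be compared between the 3 groups by Student t-tests". The sample size section reads these as two-arm comparisons: "with 20 patients per arm; effectively 40 for t-tests between groups".

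The Intervention section lists ODI, VAS, EQ-5D, Health State Scale and PCS, with PROMIS scales optional. Aim 1 also gives expected changes for SF-12 MCS and NRS. Investigation schedule and follow-up sets five post-operative visits: 6 weeks, 3 months, 6 months, 1 year and 2 years.

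The hypothesis is that outcomes in the BMAC arm "will be similar to the compared BMP group and control group at 24 months postoperatively". The Aim 1 analysis does not give that visit priority. An overall test appears only for the Aim 2 laboratory values: "One-way ANOVA and Student's t-tests will compare significant values between the 3 groups". A regression on reaching MCID is planned in Aim 1, but it is not described as a gate for the t-tests.

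**The concern.** A t-test takes two groups, so comparing three arms means three tests for each instrument at each visit. The plan does not say which of these carries the conclusion or how many may be significant by chance. If the arms truly perform alike, as the hypothesis holds, the stated analysis is still likely to give some nominally significant differences, and the plan has no rule on whether they count. The instrument or visit to emphasise could then be chosen after the results are seen. The alpha of 0.05 in the two sample size sections describes one comparison, not this set.

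**Working it through.** **The plan's own figures.** Sample Size Justification takes SD 10 and an equivalence margin of 12.8 ODI points: "given 90% power and alpha=0.05, we would need 14 patients per group". For a margin of 6 it gives 59 per group.
- Two one-sided tests: n = 2 x [SD x (z(0.95) + z(0.95)) / margin]^2.
- Margin 12.8: 2 x (10 x 3.290 / 12.8)^2 = 13.2, so 14.
- Margin 6: 2 x (10 x 3.290 / 6)^2 = 60.1, so 61.
- A two-sided two-sample t-test calculation gives 13.9 and 59.4.

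Both routes land within two patients of the stated figures. They allow for one comparison and make no allowance for several.

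**Number of tests.** 3 pairs x 5 visits x 5 instruments = 75. At 5% each, 75 x 0.05 = 3.75 false positives are expected if the arms are identical, whatever the correlations.

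**Chance of at least one false positive.** If all 75 were independent it would be 1 - 0.95^75 = 97.9%, which is only a bound. Identical arms were simulated with multivariate normal data, 17 per arm (the plan's expected completers), two-sided pooled t-tests and 10,000 trials per setting. All correlations are assumptions.

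| Outcomes tested | Correlation between instruments / between visits | Chance of at least one p < 0.05 |
|---|---|---|
| 1 instrument, 1 visit | not applicable | about 12% |
| 1 instrument, 5 visits | - / 0.5 to 0.7 | 40% to 33% |
| 5 instruments, 5 visits | 0.5 / 0.5 | 86-87% |
| 5 instruments, 5 visits | 0.5 / 0.7 | 78-79% |
| 5 instruments, 5 visits | 0.7 / 0.7 | 70% |
| 5 instruments, 5 visits | 0.8 / 0.8 | 57% |
| 5 instruments, 5 visits | 0.9 / 0.9 | 41% |

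Results with 20 per arm are nearly the same. A between-visit value of 0.5 is a natural reference. Change scores share one baseline, and with equal variances and equal pairwise correlations two such scores correlate at (1 - r) / [2(1 - r)] = 0.5.

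**Sensitivity to the instrument count.** If Health State Scale is part of EQ-5D and only four instruments count, there are 60 tests and the chance is 65% (0.7/0.7) to 81% (0.5/0.5). With SF-12 MCS and NRS added to the five, it is 77% (0.7/0.7) to 86% (0.5/0.7).

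**What an overall test achieves.** For one instrument at one visit, requiring a significant three-arm F-test before reading the pairs gives a simulated error of about 5%. Applying the F-test separately in all 25 instrument-by-visit cells still leaves about 41-56% at correlations of 0.7/0.7 to 0.5/0.5. A lead comparison is therefore needed as well.

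**Aim 2.** The marker list comes to about 15 after repeats are removed. With t-tests read only after a significant ANOVA for that marker, the chance of at least one false positive is about 37-46% at assumed between-marker correlations of 0.5 to 0.3.

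**How large a chance ODI difference would be.** With SD 10 and 17 per arm, the standard error is 10 x sqrt(2/17) = 3.43. The two-sided 5% critical value on 32 degrees of freedom is 2.037, so p < 0.05 begins at 2.037 x 3.43 = 7.0 points.

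**The case against.** The strongest reply is that a primary endpoint is named and these tests lie outside it. That stands. A reader might infer from the layout of Aim 1 that the primary analysis carries a 70-87% error rate. The documents do not support this, because the t-tests are attached to the clinical change scores and none is assigned to fusion. Leaving supportive outcomes unadjusted in a 60-patient single-site trial is also common. Against that, the hypothesis covers outcomes broadly at 24 months, one of the two sample size arguments rests on ODI, and nothing labels these comparisons as descriptive. The exploratory analysis in the Data analysis plan concerns distributions and outliers.

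A second inference would be that any chance significant difference refutes similarity. That does not follow. A difference of 7.0 ODI points lies inside the plan's 12.8-point margin, though outside its 6-point alternative.

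Third, the Aim 2 sentence could be taken to mean ungated t-tests on every marker, which would give about 68-79%. The sentence names ANOVA and can fairly be read as t-tests following a significant ANOVA, so that figure should not be used.

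Finally, the size depends on correlations that the documents do not give. At 0.8-0.9 the chance falls to 57-41%, so a false positive is not very probable under every assumption. Only the expected count of 3.75 is free of them.

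**Conclusion.** The point holds for the Aim 1 clinical outcomes. The stated method gives about 75 tests and about 3.75 expected false positives if the arms are identical and each test is at 5%. The chance of at least one is 70-87% at correlations of 0.5-0.7 and about 41% at 0.9, still far above 5%. This rests on a per-test two-sided 5% level (Aim 1 states none), about five instruments, and the assumed correlations. It does not show that the primary fusion analysis is affected, nor that one significant clinical difference would disprove similarity. For Aim 2 the gap is smaller: the gate is not stated clearly, and even with it the marker results can only be exploratory. It should be corrected, but it is not a flaw in the primary endpoint.

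**What to change.** - Keep CT fusion at 1 year as primary. Name ODI at 24 months as the lead clinical comparison; the visit comes from the hypothesis and the instrument from Sample Size Justification.
- Replace the visit-by-visit t-tests with one repeated-measures model per instrument: arm, visit and arm by visit, with the baseline score as covariate.
- Report the pairwise 24-month ODI differences with confidence intervals against one equivalence margin chosen in advance from the two in the plan, whatever the overall test shows. A non-significant test does not show similarity.
- Allow a claim of a difference in ODI at 24 months only after a significant three-arm test at that visit. With exactly three groups this holds the error over the three pairs at 5%.
- Report other visits and instruments as estimates with 95% intervals and no significance claims.
- In Aim 2, state that t-tests follow only a significant ANOVA, report every marker, and label the results exploratory.

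The cost is a change of analysis wording and slightly more analysis work. No patients, visits or procedures are added. The downside is that fewer differences can be claimed as significant.

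### The HRQOL analyses leave out the collected baseline score, and the regression on reaching MCID has too few expected responders for its terms

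*Combined protocol and SAP*

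**What the plan says.** The Data Analysis section, under Aim 1, gives two analyses of the health-related quality-of-life (HRQOL) measures. The first uses change scores: "Differences from preoperative visit to post-operative time points will be compared between the 3 groups by Student t-tests". The second is a multivariate regression "controlling for age, sex, race, and charlson comorbidity index, will be performed to determine the effect of treatment on reaching MCID values". Neither lists the baseline value of the measure as a covariate, and no baseline-adjusted linear model or mixed model appears elsewhere.

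The Intervention section places ODI, VAS, EQ-5D and PCS among the pre-operative measures, and the inclusion criteria require an ODI above 30%. Baseline ODI is therefore available for every patient.

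Aim 1 gives the expected change as "ODI from 33.42 (SD:6.22) to 26.75 (SD:8.19"). The Sample Size Justification supplies the only MCID value in the document: "If the standard deviation for each group was assumed to be 10 and equivalence as within 12.8 (MCID"). On numbers, the Sample Size Analysis says "by enrolling 20, we expect at least 17 in each group".

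**The concern.** A patient's baseline score usually predicts the follow-up score and limits how far the patient can improve. Leaving it out of every HRQOL analysis gives up precision at no saving, because the data are already collected.

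The only adjusted analysis also turns a continuous score into responder or non-responder and spreads few responders over several covariates. The trial's hypothesis is that the arms are similar. An imprecise model that shows no arm effect could then be misread as support for similarity.

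**Working it through.** **Inputs from the documents.** ODI mean (SD) 33.42 (6.22) before and 26.75 (8.19) after surgery, so the mean improvement is 33.42 − 26.75 = 6.67; ODI MCID 12.8; three arms; 20 per arm with 85% completion; entry at ODI above 30%.

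**Assumptions.** The pre-post correlation r is not given, so 0.3, 0.5 and 0.7 are used. Scores are taken as normal. Reaching MCID is taken as a binary outcome in a logistic model, with 12.8 points applied to ODI. Race coding is not stated, so one to four terms are allowed.

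**The plan's own figures.** 20 × 0.85 = 17 per arm, or 51 in total, as stated. For "given 90% power and alpha=0.05, we would need 14 patients per group", two one-sided tests give 2 × (10 × (1.645 + 1.645)/12.8)² = 13.2, so 14. For "if we assume equivalence as within 6 points, we would need 59 patients per group", the same formula gives 61, and the ordinary two-sided formula gives 2 × (10 × (1.960 + 1.282)/6)² = 58.4, so 59. Both stated sizes are reproduced to within two patients.

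**Precision of change scores against baseline adjustment.**
- Change-score variance: 6.22² + 8.19² − 2r × 6.22 × 8.19.
- Baseline-adjusted residual variance: 8.19² × (1 − r²).
- With baseline restricted to ODI above 30: 29% of a normal distribution with mean 33.42 and SD 6.22 lies below 30. The remainder has SD 4.40. With slope b = r × 8.19/6.22, the change-score variance becomes (1 − b)² × 4.40² + 8.19² × (1 − r²).

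| r | SD of change | Adjusted SD | Variance reduction | Reduction, ODI > 30 | Slope b |
|---|---|---|---|---|---|
| 0.3 | 8.67 | 7.81 | 19% | 10% | 0.40 |
| 0.5 | 7.40 | 7.09 | 8% | 4% | 0.66 |
| 0.7 | 5.87 | 5.85 | 1% | 0.4% | 0.92 |

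The two methods break even at r = 6.22/8.19 = 0.76. The ODI difference detectable with 80% power at 17 per arm (unrestricted baseline) is 8.33, 7.11 and 5.64 points with change scores, against 7.51, 6.82 and 5.62 with adjustment.

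**Expected responders.** P(improvement ≥ 12.8) = 1 − Φ((12.8 − 6.67)/SD of change). Arm takes two terms, and age, sex and Charlson index one each. With one to four race terms the model has six to nine.

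| r | Share reaching 12.8 | Responders of 51 | Responders if ODI > 30 | Per term (six terms) |
|---|---|---|---|---|
| 0.3 | 24% | 12.2 | about 15 | 2.0 to 2.5 |
| 0.5 | 20% | 10.4 | about 12 | 1.7 to 2.0 |
| 0.7 | 15% | 7.6 | about 8 | 1.3 |

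More race terms lower these ratios; with nine terms the unrestricted values are 1.4, 1.2 and 0.8. The most favourable case, in which half of the patients respond, gives 51/2/6 = 4.3 per term.

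**Simulation** (17 per arm, 1,500 runs per setting, r = 0.3, 0.5, 0.7). For a true 6-point ODI difference, power was 0.49, 0.64 and 0.82 with change scores; 0.58, 0.66 and 0.82 with baseline adjustment; and 0.30, 0.37 and 0.48 with the logistic MCID model. With no true difference, the logistic model was not estimable or quasi-separated in about 5%, 10% and 27% of runs. These percentages depend on how the covariates are coded.

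**The case against.** A reader might infer that change scores leave chance baseline imbalance uncorrected, or bias the comparison. They do neither. A change score subtracts baseline with slope 1, whereas the best slope on the plan's SDs is 0.40, 0.66 or 0.92. Imbalance is therefore over-corrected, by 0.60, 0.34 or 0.08 points per point, and under randomisation the comparison stays unbiased. The case for adjustment is precision alone. The gain is modest: at r = 0.5 the simulated power is 66% against 64%, and the entry rule on ODI shrinks it further.

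A reader might also infer that the MCID regression is bound to fail or can say nothing. The calculation supports less than that: an imprecise estimate in most runs and no usable one in some. The responder count is conditional too. It depends on r, on race coding and on the preliminary ODI figures. Aim 1 speaks of MCID values for several measures and takes their definitions from an outside source; the 12.8 points come from the Sample Size Justification and apply to ODI only. The model type is inferred, since the text says only multivariate regression. Responder rates for the other measures cannot be worked out from the document.

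Finally, the plan already has a continuous HRQOL comparison beside the MCID regression, and its primary outcome is CT fusion at 1 year. These objections limit the size and priority of the point. They do not remove the sparseness, which holds even if half of the patients respond, or the omission of a baseline score already in hand.

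**Conclusion.** The point holds as a secondary-outcome matter. The HRQOL analyses omit the collected baseline score. For the change-score t-tests the cost is a small to moderate loss of precision: 19%, 8% or 1% of variance at r = 0.3, 0.5 or 0.7, or 10%, 4% or 0.4% with baseline restricted to ODI above 30%. The MCID regression is too sparse for its covariates. About 8 to 15 responders of 51 for six or more terms is roughly 1 to 2.5 per term, with a ceiling of 4.3. These figures rest on the preliminary ODI means and SDs, normality, the assumed r, a binary outcome and the 12.8-point threshold. The documents do not support a claim of bias, of a large gain from adjustment, or of harm to the primary fusion analysis.

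**What to change.** For each HRQOL measure with a collected baseline, replace the change-score t-tests with a linear model of the follow-up score on arm (three levels) and that measure's baseline. Report BMAC versus BMP and BMAC versus autograft, each with its confidence interval, at the 24-month time point in the hypothesis. For ODI, read the intervals against one margin fixed in advance; the Sample Size Justification offers both 12.8 and 6 points, and the sponsor must choose. Report MCID response by arm descriptively, or with the baseline score as the only covariate.

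First reconcile the measure lists: SF-12 MCS and NRS appear under Aim 1 but not among the pre-operative measures in the Intervention section.

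No new data are needed for ODI, VAS, EQ-5D or PCS. The cost is revised analysis text plus three decisions to be made before the data are analysed: the time point, the ODI margin and the list of measures.

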### Aim 2: Basic Science Study

Lab analysis of aspirate quality will quantify density of CBC + differential (WBCs, platelets, Hct...), CD34+ cells, cell viability and CFU-f,,Mesenchymal Stem Cells, Colony-Formung Units, CD13, CD 14, CD29, CD34, CD44, CD45, CD73, CD90, and CD105. One-way ANOVA and Student's t-tests will compare significant values between the 3 groups

The lab analysis will be performed as per routine practice Harvest Technology, a Terumo BCT company.

PI: [name]

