### Rationale

Biologics are almost universally used as an adjunct in spinal fusions for osteoconductive (ability to serve as scaffold for bone growth), osteoinductive (ability to stimulate bone growing cells), and osteogenic (bone growth cells creating new bone) effects. However, the use of BMP is marginally very expensive and has well documented complications such as cancer, wound complication, and increased immediate post-operative pain. BMP is a commonly used adjunct for minimally invasive surgeries of the lumbar spine for its osteoconductive, osteinductive, and osteogenic effects without the need for autologous bone graft. Recent studies, specifically the study by [name]. using BMAC with allograft, and the study by Gan et al. using BMAC with beta-tricalcium phosphate during spinal fusion procedures have produced positive results comparable to BMP results. In addition, several recent studies using BMAC to treat bone non-unions and osteonecrosis (abnormal bone death) have been positive. Therefore, it is believed that BMAC with allograft has the same osteoconductive, osteoinductive, and osteogenic effects as BMP without including the same complications. Previous research conducted at our own institution has demonstrated clear efficacy in the usage of bone marrow aspiration and concentration for the treatment of high risk adult spinal deformity patients relative to iliac crest, in a randomized manner. This has been tremendously helpful in our attempt to reduce inefficiencies in the cost of patient. This study intends to further investigate and compare the efficacy and long term effects of anterior lumbar spinal fusions with BMAC and allograft to that of BMP in 2-4 level lumbar spine surgical cases. This study also attempts to enhance our understanding of the cellular mechanisms that correlate with outcomes, a point of deficiency in previous studies, by adding a cellular analysis component. Use of BMAC and allograft may be an alternative to BMP that will limit BMP's increased price, known increase of complications, and foreign antibodies. It is anticipated that there will be an increase in minimally invasive spine surgeries for lumbar degenerative disease which will expand the role and use of biologics due to suboptimal successful fusion rates without their usage. This increase in minimally invasive surgery has been reflected in the busy practices of the coinvestigators of this trial who wish to study the comparative efficacy of the 2 main biologics currently in use as their standard practice.

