### Randomization Process

The process of randomization will be computerized and completed by an individual not associated with the study. The randomization will be performed at 1:1:1 ratio between the three arms. Sequenced and sealed envelopes or a similar randomization technology approach will be used. Given posterior, anterior and anterior-posterior surgical techniques will be randomly included in the three study arms, we anticipate equal stratification. However, if study arms show predominance to one surgical approach, attempt will be made to increase enrollment of patients of the unbalanced surgical approach.

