  - 1. Pre-operative measures: narcotic usage, and health-related quality of life measures previously definedIntra-operative measures: intra-operative and perioperative blood loss, length of stay, complications
  - 2. Post-operative measures: fusion status at 1 year via CT scan, and health-related quality of life measures previously defined, length of stay, radiological outcomes, complications
- The patient and reviewer [of the clinical outcomes as well as the radiographic analysis postoperatively] will be blinded to the patient's treatment.

All materials procured from Harvest® BMAC System is FDA approved:

- Collection of Bone Marrow Aspirate Concentration (autologous adult stem cells) for Fusion
  - Bone Marrow Aspirate (BMA) will be aspirated from the anterior iliac crests using an 11 gauge 5 side-hole Jamshidi needle and a 60 mL syringe flushed with heparinized saline. Following a midline incision, the needle will be directed at about 30° to the vertical and parallel to the plane of the crest and inserted to a depth of approximately 5 to 8 cm (Figure 1). 1 mL will be sent for cellular analysis.

Figure 1

- Sixty mL of BMA will be aspirated while rotating and slowly withdrawing the needle toward the cortex. This step will be repeated on the contralateral ileum for a total of **60**, **120**, **or 180** mL of BMA. The BMA is then pooled into a blood bag containing Anticoagulant Citrate Dextrose Solution (ACD-A).
- The BMA will then be placed into the SmartPrep® Bone Marrow Concentrate (BMACTM, Harvest Technologies Corp., Plymouth, MA) system and concentrated in 15 minutes to a final volume of **10**, **20**, **or 30 mL**.
- The BMAC will then be combined with packed allograft cancellous bone chips using the Graft Delivery Pack (GDP, Harvest Technologies Corp.) yielding two or three 10 mL surgeon constructed bone logs (Figure 2). The allograft bone will be obtained routinely from the bone bank in the operating suite.

PI: [name]

Figure 2

• The allograft logs will be placed in the lateral gutter and interbody cages.

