#### rhBMP-2 Fusion

- Two mL of BMA will be aspirated in identical procedure to the BMAC group for comparison of aspirate quality.
- For patients selected to receive BMP, 12 mL BMP will be applied at the surgical site of the interbody fusion using a collagen sponge following manufacturer's directions.
- BMP kit use per level:
  - o 1 Level Fusion: Extra small kit (1.4 cc)
  - o 2 Level Fusion: Small Kit (2.8cc)
  - o 3 Level Fusion: (4.2 cc)
  - o 4 Level Fusion: Medium Kit (5.6cc)
  - o 5 Level Fusion: (7.0 cc)

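### Aim 2 tests aspirate markers between randomised arms, which is at most a balance or sampling check, and plans no analysis of how the cells relate to outcomes

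*Combined protocol and SAP*

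**What the plan says.** **The question.** The Rationale says the study will "enhance our understanding of the cellular mechanisms that correlate with outcomes, a point of deficiency in previous studies, by adding a cellular analysis component". The Sample Size Justification returns to the subject when it lists what earlier studies do not provide, including "the association between clinical outcomes and concentration of MSCs and CFUs".

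**The analysis.** Aim 2: Basic Science Study names a blood count with differential followed by "CD34+ cells, cell viability and CFU-f,,Mesenchymal Stem Cells, Colony-Formung Units, CD13, CD 14, CD29, CD34, CD44, CD45, CD73, CD90, and CD105". Its whole analysis is "One-way ANOVA and Student's t-tests will compare significant values between the 3 groups". It does not define which values count as significant and gives no multiplicity rule.

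**Allocation and sampling.**
- Randomization Process: "The randomization will be performed at 1:1:1 ratio between the three arms".
- BMAC arm (Intervention): "1 mL will be sent for cellular analysis". This comes before the pooling and concentration steps.
- BMP arm (rhBMP-2 Fusion): "Two mL of BMA will be aspirated in identical procedure to the BMAC group for comparison of aspirate quality".
- Control arm (Control Fusion): marrow is also processed for data, but the sample's volume and technique are not given.

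**Elsewhere.** The regression in Aim 1 models the effect of treatment on reaching MCID, with age, sex, race and a comorbidity index as covariates. No marker enters it. The Data analysis plan covers distributions, transformations and imputation only.

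**The concern.** The question and the test do not match. The question is whether patients with richer marrow do better. The test asks whether patients allocated to different grafts had different marrow at surgery. Randomisation makes the expected answer to the second question no, and neither answer informs the first.

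Two things are at stake. A chance or sampling difference in a marker could be reported as a biological finding about the grafts. And the samples could be taken and assayed without the mechanistic question ever being analysed, or with an analysis devised only after the data are seen.

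**Working it through.** The documents give no power, alpha or sample size for Aim 2, so there is no Aim 2 figure to reproduce. The one framing figure needed is the number of completers in Sample Size Analysis: 20 × 0.85 = 17 per arm, which reproduces and gives 3 × 17 = 51 in all.

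**Step 1: is there a treatment effect to find?** Allocation is random, the marrow is the patient's own, and it is drawn before any graft could act on it. The expected difference between arms is therefore zero if the marrow is sampled alike. Like sampling is stated for BMP against BMAC. It is not stated for control.

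**Step 2: false positives.** Counting WBC, platelets and haematocrit, 17 items are named. About 15 are distinct if CD34+ and CD34 are one marker and CFU-f and colony-forming units are one. Data Monitoring shortens the assay list to CBC, CD34+ and CFU-F, so three to five tests is also a fair reading. With k independent ANOVAs at 0.05, the chance of at least one false positive is 1 − 0.95^k:

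| k | Chance |
|---|---|
| 3 | 1 − 0.857 = 14% |
| 5 | 1 − 0.774 = 23% |
| 15 | 1 − 0.463 = 54% |

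These count the ANOVAs only. Unadjusted pairwise t-tests would add to them; positive correlation between markers would reduce them.

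**Step 3: what could an association analysis detect?** By Fisher's z, r = tanh((z for alpha + 0.842)/√(n − 3)) at 80% power. The z for alpha is 1.960 at two-sided 0.05 and 2.241 at two-sided 0.025 (Bonferroni for two markers).

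| Patients | One marker | Two markers, Bonferroni |
|---|---|---|
| 51 (all arms) | tanh(2.802/6.928) = 0.38 | tanh(3.083/6.928) = 0.42 |
| 34 (BMAC and control) | tanh(2.802/5.568) = 0.46 | tanh(3.083/5.568) = 0.50 |
| 17 (one arm) | tanh(2.802/3.742) = 0.63 | not calculated |

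Adjusting for baseline ODI and two arm indicators replaces n − 3 by n − 6. With 51 patients and one marker this gives tanh(2.802/6.708) = 0.39, so the adjustment costs little.

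**Step 4: could fusion carry the analysis?** Criteria for Action cites fusion rates of 94% with BMP-2 and 85% with marrow aspirate, so non-fusion is 6% to 15%. Among 51 completers that is 51 × 0.06 = 3.1 to 51 × 0.15 = 7.7, or about 3 to 8 non-unions. This is too few for a logistic model with several markers, arm and interactions. Patients who refuse the CT leave the primary analysis (Costs to the Subject), which can only reduce the count.

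**The case against.** The between-arm comparison has a stated purpose. The rhBMP-2 Fusion section takes the BMP-arm sample to compare aspirate quality, and Aim 2 does so. The association question stands in the Rationale only: the Sample Size Justification mentions it as a gap in earlier work, and the hypothesis and Study Objective omit it. This stands, and it makes the point a secondary one. It does not supply the missing analysis.

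Three stronger readings are tempting, and the documents do not support them.

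- *Marrow is taken the same way in all three arms, so Aim 2 can yield nothing but false positives.* The identical procedure is stated for BMP against BMAC only. Control sampling is undescribed, so a real difference due to sampling is possible. That would be an artefact, not a false positive, and a balance check might usefully reveal it.
- *The arms are sampled at 1 mL and 2 mL.* These are unlike quantities. In the BMAC arm 1 mL is the portion sent to the laboratory out of 60, 120 or 180 mL drawn; in the BMP arm 2 mL is the amount drawn. The plan does not say when in the larger draw the 1 mL is taken.
- *A false positive is more likely than not.* The 54% needs 15 independent markers, and the list visibly overlaps.

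It is also fair to object that the association analysis has limits. Pooling to 51 includes BMP patients, whose sampled marrow is not described as part of their graft. The BMAC-arm sample is described before concentration, so its density is not the cell dose delivered. Both limits stand and belong in the text of the plan.

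**Conclusion.** The concern holds in this form: the reason given for the cellular component is its relation to outcomes, and no planned analysis examines that relation. The planned between-arm tests are at most a balance or sampling check, most firmly so for BMAC against BMP. A significant result would reflect chance or sampling and would not be evidence of mechanism.

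The false-positive risk without adjustment is 14% to 54% for three to 15 independent ANOVAs, and lower under positive correlation. The expected null rests on randomisation and like sampling. The latter is stated for two arms and is an assumption for the third. The detectable correlations assume 17 completers per arm, each with both a usable sample and a 1-year ODI.

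The plan should be amended, but the primary fusion endpoint does not depend on Aim 2. A reader might infer that fusion is the natural outcome for the marker model. The plan's own fusion rates leave too few non-unions for that.

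**What to change.** Rewrite the Aim 2 analysis as follows.

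1. Show aspirate values by arm descriptively, without tests. State how and at what point of the draw the analysed sample is taken in each arm, including control.
2. Make the formal analysis a linear regression of 1-year ODI on the log density of one or two markers named in advance, adjusted for baseline ODI and arm. CFU-f and CD34+ are natural candidates because Data Monitoring lists both. Control multiplicity if two are used.
3. Label as exploratory the marker-by-arm term, the fit restricted to arms whose graft contains marrow, and any comparison of markers with fusion.
4. State the detectable correlations: about 0.38 with 51 patients (0.42 with two markers) and 0.46 with 34. State also that the sample is described before concentration and does not measure the cell dose delivered in the BMAC arm.

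The cost is small. The samples and ODI scores are already planned, so the change is one of wording, made before the data are analysed. Fewer markers are formally tested, and only moderate to large associations are detectable.
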